3.8 Schedule of Events

Table 1 below describes the daily schedule of events from Screening Visit 1 through End of the Study Visit 9.

Table 1: Daily Schedule of Events from Screening Through Visit 9

Assessments	Screening	Placebo	Treatment				Un Scheduled Visit	End-of-Study / Early Termination
Week	up to -6	-2	0	1	2	4	8	12
Days	Up to -42	-14	0 [±] 4	7 [±] 4	14 [±] 4	28 [±] 4	56 [±] 4	84 [±] 4
Visit	1	2	3	4	5	6	7	8
Written informed consent	X						Un Scheduled	9
Collection of Demographics	X							
Inclusion/ Exclusion	X							
Medical history	X							
Concomitant medication	X	X	X	X	X	X		X
Complete physical examination	X		X				X	(X ¹)
Height and weight and BMI	X							
Weight		X	X	X	X	X		X
Urine pregnancy	X	X	X		X	X		X
Serum pregnancy								
FSH ³	X							
Morning treatment in clinic		X	X	X	X	X	X	X

Medication dispensing		X	X	X	X	X	X	
Medication compliance check			X	X	X	X	X	
ECG	X							(X ¹)
Vital signs ⁴	X	X	X	X	X	X	X	(X ¹)
Clinical laboratory evaluations ⁵	X		X		X	X	X	X
Fasting blood glucose and fasting Insulin ⁶		X	X		X	X	X	(X ¹)
Self-monitored fasting morning blood glucose ⁷		X	X	X	X	X	X	
Adiponectin			X		X	X	X	X
HbA1C	X				X	X	X	X
Blood lipids: Total cholesterol, LDL, HDL, Triglycerides				X	X	X	X	
Fibroscan Test	X		X			X		
MRI PDFF	X					X		
Viral serology ⁸	X							
TSH	X							
AE/SAE assessment ⁹	X	X						

¹Only if investigator deems necessary

²Blood samples taken prior to dosing in clinic and snack provided after 30-45 minutes at V2, 3, 6, 7, and 8³Vital signs (blood pressure, heart rate, oral temperature). Vital signs will be measured in the sitting position after at least 5 minutes of rest.

³For females of non-childbearing potential, FSH levels will be tested if results are not available

⁴Vital signs (blood pressure, heart rate, oral temperature). Vital signs will be measured in the sitting position after at least 5 minutes of rest.

⁵Chemistry and hematology: electrolytes, Blood Urea Nitrogen (BUN), international normalized ratio (INR), creatinine, glucose, bilirubin, Liver Function Tests (LFTs) and Complete Blood Count (CBC)

⁶Fasting blood glucose and insulin will be used to determine Homeostasis Model Assessment (HOMA) estimates.

⁷Self-monitoring (finger-stick) of fasting blood glucose will required 3 days weekly in the morning, before breakfast, and recorded in patient diaries.
⁸HCV-Ab (hepatitis C virus antibody), HBsAg (surface antigen of the hepatitis B virus), HBcore-total (total hepatitis B core antibody), anti-HIV Ab (human immunodeficiency virus antibody).

⁹Adverse events will be collected throughout the study beginning from the time the patient signs the consent form until the EOS evaluations

4 STUDY SUBJECT SELECTION

4.1 Inclusion Criteria

Each subject must meet all of the following criteria to be eligible for the study:

Inclusion Criteria

1. Male or female aged 18-70 years.
2. BMI ≥ 25
3. Known type 2 DM according to American Diabetic Association (one of the three needed): Fasting Plasma Glucose ≥ 126 mg/dl or 2h postprandial (PG) following 75g OGTT ≥ 200 mg/dl or HbA1C $> 6.5-11\%$ ²⁸ or on treatment with at least one and no more than-three of the following oral anti-diabetic medications metformin, sulfonylurea, DPP-4 inhibitors, oral GLP-1 receptor agonists (semaglutide), SGLT-2 inhibitor or Thiazolidinediones (TZDs).
4. Diagnosis of NAFLD by non-invasive determination of hepatic steatosis grade S1, defined as hepatic steatosis $> 8\%$, by MRI- PDFF and CAP FibroScan ≥ 238 dB/m.
5. Liver enzyme abnormalities: ULN ≤ 5 times.
6. Fibrosis score $1 \leq F \leq 3$ as defined by FibroScan measurement (Liver stiffness measurement, LSM) of $6 \leq LSM \leq 12$ kPa.
7. Signature of the written informed consent.
8. Negative pregnancy test at study entry for females of childbearing potential.
9. Females must have a negative urine pregnancy test result at screening, prior to the start of the run-in period, at initiation of active dosing and every 4 weeks following till the end of the study. A negative urine and serum pregnancy test must be obtained prior to active dosing. Males and females of childbearing potential must use two methods of contraception, one of which must be a highly effective method from the time of screening to the last dosing study visit (22 weeks).

Highly effective methods include:

- o combined (estrogen and progestogen containing) hormonal contraception (oral, intravaginal or transdermal) associated with inhibition of ovulation
- o progestogen-only hormonal contraception (oral, injectable or implantable) associated with inhibition of ovulation
- o intrauterine device (IUD)
- o intrauterine hormone-releasing system (IUS)
- o bilateral tubal occlusion

Acceptable methods include:

Double barrier methods of contraception include male condoms plus spermicide, diaphragm with spermicide plus male condom, cervical cap with spermicide plus male condom. If a subject is not usually sexually active but becomes active, he or his partner should use medically accepted forms of contraception. Sperm donations will not be allowed for the duration of the study and for 90 days after the last dose of study drug. Females of non-childbearing potential are defined as postmenopausal who a) had more than 24 months since last menstrual cycle with menopausal levels of FSH (FSH > 40), b) who are surgically menopausal (surgical sterility defined by tubal occlusion, bilateral oophorectomy, bilateral salpingectomy or hysterectomy).

10. For hypertensive patients, hypertension must be controlled by stable dose of anti-hypertensive medication for at least 2 months prior to screening (and the stable dose can be maintained throughout the study) with $BP < 150/ < 95$ mmHg
11. Patients previously treated with vitamin E (>400 IU/day), Polyunsaturated fatty acid (>2 g/day) or Ursodeoxycholic acid fish oil can be included if drugs are stopped at least 3 months prior to enrolment and up to the end of the study.

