Life-style modifications are effective but adherence is difficult to maintain.¹⁷ Bariatric surgery can be performed in selective obese patients, but is too drastic to be the treatment of choice and thus it is not recommended for treating NASH.¹⁸ Vitamin E has been effective in treating nondiabetic NASH patients without cirrhosis.¹⁹ The long-term safety and efficacy of pioglitazone are not clear in NASH.^{20, 21} Metformin²², ursodeoxycholic acid, omega 3 fatty acids, and statins are not considered as therapy for NAFLD/NASH patients.^{1, 21}

TYPE 2 DIABETES and NAFLD/NASH

Type 2 DM involves failure of the action and utilization of insulin within the body. Type 2 sufferers have an endogenous resistance to insulin. The disease appears when they fail to manufacture sufficient insulin levels to overcome this resistance. This relative lack of insulin eventually leads to chronic hyperglycemia.

Traditionally, type 2 was known as “adult-onset diabetes” (with type 1 being referred to as “juvenile-onset” diabetes) as it generally struck adults, usually overweight, of age 45 and over. However, in recent years, the incidence of type 2 DM has skyrocketed—to the extent that it is now being termed a global “pandemic.” Type 2 DM is strongly correlated with obesity, and so this disproportionate increase is considered a reflection of the twin ills of modern life—overeating/obesity and decreased physical activity.

The 2014 CDC National Diabetes Statistics Report estimated that 29.1 million people or 9.3% of the US population have diabetes; 21 million diagnosed and 8.1 million undiagnosed.²³ Another 86 million (37% of US adults aged 20 years and older) people were estimated to suffer from pre-diabetes, a condition that increases the risk of developing type 2 DM—the more common form of the disease—as well as heart disease and stroke.

Comparable statistics may be found in both developed and developing countries around the world as the frequency of diabetes continues to rise. Global prevalence of diabetes is now estimated at more than 380 million, or about 8% of the worldwide adult population according to the International Diabetes Federation. Type 2 DM represents 85-95% of both present and future cases.²⁴

As noted above, the prevalence of NAFLD can be as high as 90–95% in obese individuals and up to 70% of patients with type 2 DM develop NAFLD.²⁵ In addition, they share similarities in their risk factors, pathogenic mechanisms and complications.

INSULIN TREATMENT

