Subjects will then undergo a treatment phase consisting of a treatment period of 12 weeks that will start at Visit 3 (Week 0) and outpatient visits at Weeks 1, 2, 4, 8, and 12 (final visit). At each visit, concomitant medication will be reviewed, weight will be measured, ORMD-0801 morning treatment will be administered in clinic, and sufficient quantity of medication will be dispensed to last until the next nominal clinic visit. Medication compliance check will be performed, self-monitored fasting morning blood glucose (finger-stick) will be recorded 3 days weekly in the morning and subjects' diaries will be reviewed. Vital signs (SBP/DBP, heart rate and oral temperature) will be recorded. Adverse events will be monitored and recorded.

At Visit 3, urine and serum pregnancy test will be performed for females of childbearing potential. Additional urine serum pregnancy test will be performed for females of childbearing potential at visits 6, 7 and 8. At Visit 8, subjects will have HbA1c evaluations and MRI-PDFF performed. At Visits 3 and 8, a complete physical exam and fibroscan will be performed.

The end of the study (EOS) Visit (Visit 9) will be conducted 4 weeks following the last scheduled treatment visit. Subjects concomitant medications will be reviewed, and weight will be measured. A complete physical exam and ECG will be performed and vital signs (SBP/DBP, heart rate and oral temperature) will be measured if deemed necessary by the investigator. Clinical laboratory evaluation will be performed. Fasting blood glucose, fasting insulin, HbA1c,

blood lipids and adiponectin levels will be measured. Urine serum pregnancy test will be performed for females of childbearing potential. Subject diaries will be collected and reviewed for self-monitored fasting morning blood glucose. Adverse events will be monitored and recorded. Subjects who are discontinued early from the study will complete the EOS evaluations at the time of early discontinuation.

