3.2 Screening/Visit 1 (up to week -6)

Screening process will take place at Visit 1, up to 42 days prior to enrolment. Screening activities will consist of the following:

Visit 1 (up to week -6)

- Informed consent
- Medical history
- Concomitant medication
- Complete Physical examination (PE)
- Weight and height
- ECG
- Vital signs (blood pressure, heart rate, oral temperature). Vital signs will be measured in the sitting position after at least 5 minutes of rest.
- Urine pregnancy test
- Females of non-childbearing potential FSH levels will be tested if results not available.
- Clinical laboratory evaluations
 - Chemistry: Electrolytes, Blood Urea Nitrogen (BUN), international normalized ratio (INR), creatinine, glucose level, liver function tests (LFT) including transaminases (ALT, AST), albumin, and alkaline phosphatases, creatine phosphokinase (CPK), Bilirubin
 - Hematology: Complete blood count (CBC)
 - Thyroid Stimulating Hormone (TSH)
 - HbA1C
 - Blood lipids: Total cholesterol, LDL, HDL, Triglycerides
 - Viral serology: HCV-Ab, HBsAg, HBcore-total, HBs Ab, anti-HIV Ab
- CAP - Fibroscan
- MRI-PDFF
- AE/SAE assessment

For subjects who meet eligibility criteria based on the Screening assessments, instruction will be provided on the following:

- the use of adequate contraceptive methods (see Section 4.1) for the duration of the study (Screening through End of Study (Visit 9);
- minimal use of concomitant medications during the study, if possible, and avoid prohibited medications as defined in Section 5.6;
- maintenance of usual dietary habits and avoidance of drastic changes, such as a conversion to a vegetarian diet;

- restraint from excessive alcohol use or binge drinking during the study, and restraint from drinking alcohol from 72 hours prior to all study visits;
- restraint from excessive caffeine use (i.e., more than five cups of caffeinated beverages per day) during the study.

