4.2 Exclusion Criteria

Subjects who meet any of the following criteria must be excluded from the study:

1. Patients with active (acute or chronic) liver disease other than NASH (e.g. viral hepatitis, genetic hemochromatosis, Wilson disease, alpha-1 antitrypsin deficiency, alcohol liver disease, drug induced liver disease) at the time of enrolment.
2. ALT or AST > 5 times ULN.
3. Abnormal synthetic liver function (serum albumin ≤ 3.5 gm%, INR > 1.3).
4. Known alcohol and/or any other drug abuse or dependence in the last five years.
5. Weight > 120 Kg
6. Known history or presence of clinically significant, cardiovascular, gastrointestinal, metabolic (other than diabetes mellitus), neurologic, pulmonary, endocrine, psychiatric, neoplastic disorder or nephrotic syndrome.
7. History or presence of any disease or condition known to interfere with the absorption, distribution, metabolism or excretion of drugs including bile salt metabolites (e.g. inflammatory bowel disease (IBD), previous intestinal (ileal or colonic) operation, chronic pancreatitis, celiac disease or previous vagotomy).
8. Weight loss of more than 5% within 6 months prior to enrolment.
9. History of bariatric surgery.
10. Uncontrolled blood pressure $BP \geq 150/ \geq 95$.
11. Non type 2 DM (type 1, endocrinopathy, genetic syndromes etc).
12. Patients with HIV.
13. Daily alcohol intake > 20 g/day (2 units/day) for women and > 30 g/day (3 units/day) for men.
14. Treatment with anti-diabetic medications other than at least one and no more than-three of the following medications: metformin, sulfonylurea, DPP-4 inhibitors, oral GLP-1 receptor agonists (semaglutide), SGLT-2 inhibitors, or TZDs
15. Fibrates and statins, not provided on a stable dose in the last 6 months.
16. Patients who are treated with valproic acid, Tamoxifen, methotrexate, amiodarone.
17. Chronic treatment with antibiotics (e.g. Rifaximin).
18. Homeopathic and/or Alternative treatments. Any treatment must be stopped before the screening period.
19. Uncontrolled hypothyroidism defined as Thyroid Stimulating Hormone $> 2X$ the upper limit of normal (ULN). Thyroid dysfunction controlled for at least 6 months prior to screening is permitted.
20. Patients with renal dysfunction: eGFR < 40 ml/min.
21. Unexplained serum creatinine phosphokinase (CPK) $> 3X$ the upper limit of normal (ULN). Patients with a reason for CPK elevation may have the measurement repeated prior to enrolment; a CPK retest $> 3X$ ULN leads to exclusion.

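### Eligibility sets no stable-dose period for background glucose-lowering drugs, so any liver-fat effect of a recently started one cannot be separated from ORMD-0801

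*Combined protocol and SAP*

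**What the plan says.** Inclusion 3 (synopsis and Section 4.1) accepts a patient "on treatment with at least one and no more than-three of the following oral anti-diabetic medications": metformin, sulfonylureas, DPP-4 inhibitors, oral semaglutide, SGLT-2 inhibitors and TZDs. Exclusion 14 (synopsis and Section 4.2) mirrors it: "Treatment with anti-diabetic medications other than at least one and no more than-three of the following medications". Neither mentions treatment duration or dose stability, and no other current criterion requires stable HbA1c.

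Other drugs in the same lists do have time rules:

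- Antihypertensives (Inclusion 10): "hypertension must be controlled by stable dose of anti-hypertensive medication for at least 2 months prior to screening", with the expectation that the dose can be held during the study.
- Vitamin E, polyunsaturated fatty acids and ursodeoxycholic acid (Inclusion 11): previously treated patients "can be included if drugs are stopped at least 3 months prior to enrolment and up to the end of the study".
- Lipid drugs (Exclusion 15): "Fibrates and statins, not provided on a stable dose in the last 6 months".

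The baseline MRI-PDFF belongs to screening: "Screening process will take place at Visit 1, up to 42 days prior to enrolment". The only other scan is at the end of treatment: "At Visit 8, subjects will have HbA1c evaluations and MRI-PDFF performed". Section 6.4 defines the liver-fat assessment as the difference between final and baseline MRI and Fibroscan results. There is one open-label arm, and Section 8 contains no adjustment, subgroup or sensitivity analysis by background therapy.

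**The concern.** In a single-arm before-and-after comparison, everything that acts between the two scans enters the estimated change. Eligibility rules on stable medication are one of the few protections such a design has. This protocol uses them for blood-pressure drugs, lipid drugs and supplements, but not for glucose-lowering drugs. Yet the Introduction names insulin resistance as the link between diabetes and NAFLD, which places glucose-lowering treatment close to the hypothesis under test.

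A patient who started or up-titrated such a drug shortly before Visit 1 and then held it constant meets the medication criteria and makes no on-study change that would mark them out. If the drug affects liver fat, part or all of that effect lies between the scans. At stake is the interpretation of the MRI-PDFF change, which Section 8.1 relies on when it calls the sample size sufficient to show trends in liver fat.

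**Working it through.** **1. The plan's own figure.** The sample size is up to 40 (about 20 in Israel, 10 in Belgium, 10 in the USA). Section 8.1 gives no effect size, SD, alpha or power and says the study is not powered for significance. There is therefore no calculation to reproduce, and N does not depend on this point.

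**2. Rules side by side.**

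| Background drug | Time rule | Place |
|---|---|---|
| Antihypertensives | stable 2 months before screening | Inclusion 10 |
| Vitamin E, PUFA, UDCA | stopped 3 months before enrolment | Inclusion 11 |
| Statins, fibrates | stable 6 months | Exclusion 15 |
| Glucose-lowering drugs | none; one to three drugs | Inclusion 3, Exclusion 14 |

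**3. Time at risk.** The screening scan is up to day -42 and the final scan is on day 84 ± 4. The interval is up to 42 + 84 = 126 days, or 130 with the window. If the screening scan falls as late as day -14, when the run-in starts, it is nominally 14 + 84 = 98 days. The baseline scan precedes the placebo run-in and is not repeated at Visit 3, so the run-in does not protect it. A drug started at about Visit 1 has its whole effect over that interval between the scans; one started weeks earlier has only the remainder there.

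**4. Which measures are exposed.** MRI-PDFF is the most exposed. Fibroscan is repeated at Visit 3, and fasting insulin (for HOMA) is drawn at Visits 2 and 3. Both therefore have later baselines, which could already contain part of a new drug's effect.

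**5. Size, for illustration.** If k of n patients are recent starters and each has a residual fall of d points from the background drug between the scans, the mean change is shifted by

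b = (k / n) × d.

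The documents give only n = 40. The values of k (0 to 10) and d (1 to 4 percentage points) are assumptions.

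| k of 40 | d = 1 | d = 2 | d = 4 |
|---|---|---|---|
| 0 | 0 | 0 | 0 |
| 4 | 0.10 | 0.20 | 0.40 |
| 8 | 0.20 | 0.40 | 0.80 |
| 10 | 0.25 | 0.50 | 1.00 |

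**6. Against random error.** Assume an SD of change of 3 to 5 points (also not in the documents). The half-width of a 95% interval is 1.96 × SD / √40, which is 0.93 points for SD 3 and 1.55 for SD 5. If ORMD-0801 had no effect, the chance that such an interval excludes zero is Φ(b√40/SD − 1.96) + Φ(−b√40/SD − 1.96):

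- 4 starters (b = 0.1 to 0.4): 5% to 14%.
- 8 starters (b = 0.2 to 0.8): 6% to 39%.
- The extreme, b = 1.0: 24% (SD 5) to 56% (SD 3).

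No such test is planned. The figures only show when the shift would be noticeable.

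**The case against.** The strongest objection is that the effect itself is not documented. A reader might infer from the Introduction that a permitted class is known to reduce liver fat, because pioglitazone is discussed there as a NASH treatment. The text does not go that far: "The long-term safety and efficacy of pioglitazone are not clear in NASH". It reports no liver-fat effect or time course for TZDs, and none for semaglutide or SGLT-2 inhibitors. It follows that the documents do not establish a bias towards benefit; they establish only that an effect, if present, could not be separated. This objection stands and limits the conclusion. The number of recent starters is also unknown and may be zero.

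Second, there are partial safeguards. Section 6.6 records medication from 30 days before Visit 1 and notes dose increases of concomitant drugs. Section 5.6 has the investigator evaluate concomitant medication case by case. Section 4.3 allows withdrawal when a medication would interfere with interpretation. These are real but discretionary, and none sets a stability standard. The 30-day look-back is shorter than every interval in the table of rules, and a drug started before Visit 1 and then held constant need not prompt any of them.

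Third, liver fat is secondary and descriptive in an exploratory study, and a stable-dose rule removes only one of several uncontrolled influences. That is correct. The rule would not by itself make the remaining change attributable to ORMD-0801.

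**Conclusion.** The omission is clear in the current text, in both places where the criteria appear. Following the plan exactly admits patients whose background drug may still be taking effect, and the design offers no way to separate that from ORMD-0801 on MRI-PDFF. This is a weakness of design, not merely a missing detail.

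Its size is not determined by the documents. With 0 to 10 recent starters and a residual fall of 1 to 4 points each, the spurious mean fall is 0 to 1.0 points. The lower part of that range is small against the assumed random error; the upper part could be read as a trend.

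A reader might go further and conclude that all efficacy measures are equally affected or that the primary safety result is compromised. The documents do not support either. HOMA and Fibroscan have later baselines, and safety is touched only through attribution of adverse events to ORMD-0801 or to a newly started drug.

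**What to change.** 1. **Eligibility.** Add to Inclusion 3 and Exclusion 14, in the synopsis and in Sections 4.1 and 4.2: *type and dose of all glucose-lowering medication unchanged for at least X before the screening MRI and expected to remain unchanged through Visit 8*. This follows the form of Inclusion 10. The sponsor sets and justifies X; the documents give no time course from which to derive it. Both criteria need the sentence, because background treatment is only one of the alternative ways to satisfy Inclusion 3. Medically needed changes remain allowed and are recorded. Extending the rule to Visit 8 matters because a drug started between Visit 1 and Visit 3, or during treatment, also acts between the scans.
2. **Data.** For all patients, including those already enrolled, collect the start date and last dose-change date of each glucose-lowering drug, far enough back to cover X. The CRF is not in the documents, so some of these dates may already be collected.
3. **Analysis.** Show the MRI-PDFF change separately for patients with and without stable background therapy from the start of that period through Visit 8. This is descriptive and needs no change to N.

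With the entry rule in place, k at entry is 0 and so is this bias term, provided X is long enough; later changes appear in the split. The cost is one eligibility sentence, possibly two date fields per drug, and a few candidates who wait or are not enrolled.

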Subject Selection Criteria	Inclusion Criteria 
1. Male or female aged 18-70 years.2. BMI ≥ 253. Known type 2 DM according to American Diabetic Association (one of the three needed): Fasting Plasma Glucose ≥ 126 mg/dl or 2h postprandial (PG) following 75g OGTT ≥ 200 mg/dl or HbA1C $> 6.5\text{--}11\%$²⁸ or on treatment with at least one and no more than-three of the following oral anti diabetic medications metformin, sulfonylurea, DPP-4 inhibitors, oral GLP-1 receptor agonists (semaglutide), SGLT-2 inhibitor, or Thiazolidinediones (TZDs)4. Diagnosis of NAFLD by non-invasive determination of hepatic steatosis grade S1, defined as hepatic steatosis $> 8\%$. by MRI- PDFF and CAP FibroScan ≥ 238 dB/m.5. Liver enzyme abnormalities: ULN ≤ 5 times.6. Fibrosis score $1 \leq F \leq 3$ as defined by FibroScan measurement (Liver stiffness measurement, LSM) of $6 \leq LSM \leq 12$ kPa.7. Signature of the written informed consent.8. Negative pregnancy test at study entry for females of childbearing potential.9. Females must have a negative urine pregnancy test result at screening, prior to the start of the run-in period, at initiation of active dosing and every 4 weeks till the end of the study. A negative urine and serum pregnancy test must be obtained prior to active dosing. Males and females of childbearing potential must use two methods of contraception, one of which must be a highly effective method from the time of screening to the last study visit (22 weeks). Highly effective methods include:
○ combined (estrogen and progestogen containing) hormonal contraception (oral, intravaginal or transdermal) associated with inhibition of ovulation○ progestogen-only hormonal contraception (oral, injectable or implantable) associated with inhibition of ovulation○ intrauterine device (IUD)○ intrauterine hormone-releasing system (IUS)○ bilateral tubal occlusion○ vasectomised partner (is the sole sexual partner of the WOCBP participating in the trial)○ sexual abstinence

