7.5.2 Reporting of Serious Adverse Events

In accordance with Federal regulations, Investigators will be notified of the occurrence of serious, unexpected and related adverse events.

The Investigator must report all serious adverse events to Sponsor or delegate within 24 hours of the site being notified of the event. Investigators must also report these events to the Institutional Review Board (IRB) in accordance with the IRB's reporting guidelines, within the IRB specified timeframe, or no later than 48 hours after knowledge of the event.

For submission of these events to the Israeli Regulatory Agency- the Sponsor will follow FDA regulations 21 CFR 312.32. If the event is determined to meet the requirements of IND Safety Reporting, then expedited reporting requirements to the FDA will be followed. The Sponsor may need to issue an Investigator notification, to inform all Investigators involved in any study with

the same drug (or therapy) that this serious unexpected suspected adverse reaction (SUSAR) has occurred.

Investigator Reporting Procedures

The PI or other study personnel must immediately (within 24 hours) inform Sponsor or delegate of any AE considered serious (as defined above) or otherwise medically significant. Notification should be via email or facsimile transmission of a written report signed by the PI. Notification must include the PI's assessment as to whether the event was or was not related to the use of the study medication. The Sponsor contact information is as follows:

Oramed Ltd.

[name]

Contact person at Oramed:

[name]

Email: [contact]

[contact]

The Principal Investigator must also promptly inform the governing IRB of the serious adverse event per the governing IRB's requirements.

The CRO will notify Oramed within 24 hours of receipt. Any SAE that occurred within 30 days after last dose will be followed and reported as above.

Pregnancy Reporting

If the subject or partner of a subject participating in the study becomes pregnant during the study or within 30 days of discontinuing study medication, the Investigator should report the pregnancy to Oramed within 24 hours of being notified. The Exposure In Utero form to the Investigator for completion.

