7.6.1 Potential Adverse Events Associated with ORMD-0801

Hypoglycemia and associated symptoms (e.g., weakness, dizziness, shakiness, increased sweating, palpitations, or confusion), have been associated with insulin administration, including ORMD-0801. Animal reproductive studies have not been conducted with ORMD-0801. It is not known whether ORMD-0801 can cause fetal harm when administered to a pregnant woman. It is also not known whether this product is excreted in human milk. Pregnant or breastfeeding women are excluded from this study.

Long-term animal studies have not been completed to assess whether ORMD-0801 impairs fertility.

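### The protocol sets unexplained and unequal post-dose periods for sperm donation (90 days), male contraception (about 28 days for a completer) and pregnancy reporting (30 days)

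*Combined protocol and SAP*

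**What the plan says.** Three rules deal with reproduction after the last dose.

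- **Sperm donation.** Criterion 9, in both the Synopsis and Section 4.1: "Sperm donations will not be allowed for the duration of the study and for 90 days after the last dose of study drug".
- **Contraception.** Also criterion 9: "Males and females of childbearing potential must use two methods of contraception". The period in the Synopsis runs "from the time of screening to the last study visit (22 weeks"), and in Section 4.1 "from the time of screening to the last dosing study visit (22 weeks"). Section 3.2 tells eligible subjects to use contraception "for the duration of the study (Screening through End of Study (Visit 9"). Section 3.5 puts Visit 9 at 4 weeks after the last scheduled treatment visit.
- **Pregnancy reporting.** Section 7.5.2 asks for a report within 24 hours of the investigator being notified, if a subject or a subject's partner "becomes pregnant during the study or within 30 days of discontinuing study medication". Follow-up continues to the outcome, and specified outcomes are handled as serious adverse events.

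On the background risk, Section 7.6.1 says that animal reproductive studies have not been done and that long-term animal studies of fertility are not complete. It adds: "It is not known whether ORMD-0801 can cause fetal harm when administered to a pregnant woman".

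No section explains why the three periods differ, and none carries contraception or pregnancy reporting to 90 days.

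**The concern.** A ban on donating sperm after the last dose makes sense mainly as a guard against conception. If the sponsor wants that guard for 90 days, one would expect either the same period for conception with a partner or a sentence saying why it can be shorter. The protocol has neither, although the donation rule and the contraception rule sit in the same criterion.

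What is at stake is the capture of safety information. Section 7.5.2 already treats a partner pregnancy as something to report, follow and, for some outcomes, classify as serious. A partner pregnancy that began on day 45 after a completer's last dose would trigger none of those duties. Sites would also have no stated basis for answering a male subject who asks why one rule lasts about three times as long as the others.

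**Working it through.** **Inputs.** Screening is at most 42 days before enrolment: "Screening process will take place at Visit 1, up to 42 days prior to enrolment" (Section 3.2). The run-in at week −2 falls inside that period. Dosing runs from Visit 3 (day 0) to Visit 8 (day 84, week 12; Sections 3.4 and 5.3). Visit 9 is 28 days after Visit 8 (Section 3.5). The donation ban is 90 days after the last dose (criterion 9). Pregnancy reporting is 30 days after stopping drug (Section 7.5.2).

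**Step 1: reproduce the plan's 22 weeks.**

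- Visit 9 = 84 + 28 = day 112.
- Screening to Visit 9 = 112 − (−42) = 154 days; 154 / 7 = 22 weeks. This matches.
- Screening to Visit 8 = 84 − (−42) = 126 days; 126 / 7 = 18 weeks. This does not match.
- Six weeks of screening followed by a separate 2-week run-in would give 6 + 2 + 12 + 4 = 24 weeks. This does not match either.

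So 22 weeks ends at Visit 9, as in the Synopsis and Section 3.2. The Section 4.1 wording, which names the last dosing visit, contradicts its own figure.

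**Step 2: gaps for a male subject who completes treatment.**

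| Rule | Ends, days after last dose | Gap to 90 days |
|---|---|---|
| Sperm donation | 90 | none |
| Contraception, to Visit 9 | 112 − 84 = 28 | 90 − 28 = 62 |
| Contraception, to last dosing visit (literal Section 4.1) | 0 | 90 |
| Pregnancy reporting | 30 | 90 − 30 = 60 |

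On the Visit 9 reading, contraception and reporting are both absent on days 31 to 90. Correcting the Section 4.1 wording to agree with the Synopsis therefore leaves 62 days.

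**Step 3: subjects who stop drug early but attend through Visit 9.** If drug stops on day s, contraception covers 112 − s days after the last dose. The gap is max(0, 90 − (112 − s)) = max(0, s − 22).

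| Drug stops on day | Covered after last dose (days) | Contraception gap (days) |
|---|---|---|
| 22 | 90 | 0 |
| 28 | 84 | 6 |
| 56 | 56 | 34 |
| 84 | 28 | 62 |

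A subject who leaves the study early has the end-of-study evaluations at once (Section 3.5). His contraception requirement may end then, while reporting still runs for 30 days.

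**Step 4: visit window.** The window for Visit 9 cannot be read from Table 1. If ±4 days is assumed, as at the treatment visits, contraception ends on days 24 to 32 and the gap is 58 to 66 days. Reporting during the study could then reach day 32. The picture does not change.

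**The case against.** The strongest answer is that three rules for three different acts do not contradict one another as text. The 90 days is stated for donation only and without a reason, and the protocol never calls it an exposure window. The sponsor may have set it more cautiously for reasons of its own. The fetal-harm sentence in Section 7.6.1 concerns dosing of a pregnant woman, so it sets no post-dose period for men. All of this stands. What remains is an unexplained difference within one criterion, which a sentence of rationale could also resolve.

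A reader might infer more than the documents support:

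- **That 90 days is the protocol's own exposure window, two thirds of which goes unreported.** The fraction 60/90 is correct arithmetic, but calling the 90 days an exposure window is inference.
- **That every male subject is affected by the same gap.** The 62 days applies to completers. Sections 3.7 and 4.3 allow treatment to stop early, and Section 3.7 keeps subjects stopped for glucose reasons in follow-up, where the gap shrinks or vanishes. The issue has no practical effect for men who are abstinent or whose partners cannot conceive.
- **That the safety database could contain no such pregnancies.** Section 7.5.2 sets a duty and does not bar later reports. A pregnancy that begins within 30 days but is discovered later is still reportable, because the 24-hour clock starts at notification.
- **That participants are told conflicting things.** The consent pages are not available for review, so this cannot be checked.
- **That the analysis is affected.** The planned safety tables summarise subjects' own treatment-emergent events (Section 8.2.1). Partner pregnancies after Visit 9 would not alter them.

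One sentence in criterion 9, on subjects who become sexually active, might be thought to fill the gap. It has no end date and sets no 90-day requirement.

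**Conclusion.** The point holds as a minor inconsistency in safety capture. For a male completer, days 31 to 90 after the last dose carry a donation ban with no matching contraception requirement and no duty to report a partner pregnancy. The gaps are 62 and 60 days. If Section 4.1 is read literally, the contraception gap is the full 90 days.

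This rests on three assumptions: that the last dose is taken at Visit 8, that Visit 9 falls on its nominal day, and that reporting during the study means during the subject's own participation. The first two are the nominal schedule. That the donation rule reflects a concern about conception is reasonable but not stated.

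The practical weight is low. The study enrols up to 40 patients of both sexes aged 18 to 70, the sex mix is not given, and the expected number of affected pregnancies is very small. No estimate or stopping rule depends on the point.

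**What to change.** Reconcile the post-dose periods in criterion 9 (Synopsis and Section 4.1), Section 3.2 and Section 7.5.2, and state the rationale. The length is for the sponsor to decide. If different periods are intended for donation and contraception, say so and why. In the same edit, make the Section 4.1 end point agree with its own 22 weeks.

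Align the pregnancy-reporting window in Section 7.5.2 with whatever post-dose reproductive-precaution period is kept for males. Use the existing 24-hour report and outcome follow-up, and remind subjects of it at Visit 9 or early termination.

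The cost is wording in the protocol and, where it repeats these periods, the consent form. No visit or test is added. The small downside, if the reporting window lengthens, is that sites stay open to participant-reported pregnancies for longer after Visit 9.
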